3.3.3 Handling of Unscheduled Visits

Unscheduled, retest (with the same visit number assigned), and early discontinuation measurements will be included in by-visit summaries per Section 3.3.2

In the case of a missing value at a scheduled visit, which is then followed by a non-missing value at an unscheduled assessment within the same visit window, the non-missing value at the unscheduled assessment will be used.

Data collected at unscheduled assessments might be included in baseline definitions, and in any definitions of maximum value, minimum value where appropriate.

3.3.4 Multiplicity/Multiple Comparisons

All analyses will be performed in descriptive manner, no hypothesis testing will be performed.

3.3.5 Handling of Protocol Deviations in Study Analysis

Protocol deviations will be collected, reviewed, and reconciled throughout the study. Important protocol deviations (IPDs) will be identified from the complete set of protocol deviations. IPDs are those which may significantly impact the completeness, accuracy, or reliability of the study data or that may significantly affect a participant's rights, safety, or wellbeing.

All decisions on importance will be made throughout the study and finalised before clinical data base lock.

4 STATISTICAL ANALYSIS

This section provides information on definitions, derivation and analysis/data presentation per domain.

4.1 Study Population

The domain study population covers participants disposition, analysis sets, protocol deviations, demographics, baseline characteristics, medical history, prior and concomitant medication and study drug compliance.

4.1.1 Participants Disposition and Completion Status

4.1.1.1 Definitions and Derivations

Participants disposition and completion status will be comprised of the following:

- Enrolled (screened) participants;

- Non-randomized participants (screen failures);
- Randomized participants;
- Participants who were randomized but not dosed;
- Participants who received study intervention;
- Participants who were randomized and ongoing in study (applicable to primary analysis)
- Randomized participants who completed the study.
- Randomized participants who withdrew from the study;
 - Reasons for withdrawal;

4.1.1.2 Presentation

Number and percentage of participants in the following categories will be reported: participants who were screened, non-randomized, randomized, randomized but not dosed, received study intervention, randomized and ongoing in study (applicable to primary analysis), withdrew from the study (with reasons) and who completed the study.

4.1.2 Analysis Sets

4.1.2.1 Definitions and Derivations

Refer to Section 3.2 for definition of analysis sets:

- Screened set
- Full analysis set
- Safety analysis set
- SARS-CoV-2 neutralizing antibody (nAb) analysis set.

4.1.2.2 Presentation

The number of participants included in each analysis set will be reported by treatment arm. In addition, for each analysis set, the number of participants excluded, including the reasons, will be reported.

4.1.3 Protocol Deviations

4.1.3.1 Definitions and Derivations

A detailed list of possible important protocol deviations (IPDs) and the process for reviewing them by the clinical study team will be outlined in the protocol deviations management plan (PDMP).

The medical and statistical team members will review the protocol deviation categories in a blinded fashion before the clinical database lock and be classified as important per the PDMP.

At a minimum, the following deviations categories will be included for review and classified as important for the evaluation and implementation of the study:

- Inclusion Criteria Deviations
- Exclusion Criteria Deviations
- Discontinuation Criteria for study product met but participant not withdrawn from study treatment
- Discontinuation Criteria for overall study withdrawal met but participant not withdrawn from study
- Investigational Product Deviation
- Excluded Medications taken
- Deviations to study procedure
- Other Important Protocol Deviations

4.1.3.2 Presentation

The number and percentage of participants with IPDs will be provided per protocol deviation category. The summary will be based on the Safety Analysis Set.

All important protocol deviations will be presented in a listing.

4.1.4 Demographics

4.1.4.1 Definitions and Derivations

Demographics will be comprised of age, sex, race and ethnicity.

4.1.4.2 Presentation

All Demographic data will be summarized for all participants in the Safety Analysis Set.

4.1.5 Baseline Characteristics

4.1.5.1 Presentation

Following baseline characteristics will be summarized for all participants in the Safety Analysis Set:

- Weight (kg)
- Height (cm)
- Body mass index (BMI, kg/m²)
- Sufficient medical conditions:
 - Obese, (BMI \geq 30 kg/m²)
 - Congestive heart failure
 - Chronic obstructive pulmonary disease
 - Chronic kidney disease, (GFR < 30 mL/min/1.73 m²)

- Intolerant of vaccine
- Immunocompromised state
- Previous COVID-19 vaccinations:
 - Participants previously vaccinated
 - Brand of last COVID-19 vaccine
 - Number of prior COVID-19 vaccinations received
 - Whether any bivalent booster was received or not
- Age group:
 - <60 years
 - ≥60 years

4.1.6 Disease Characteristics

4.1.6.1 Presentation

The following data on prior COVID-19 infections will be summarized for Safety Analysis Set:

- Time (days) from last COVID-19 infection reported (calculated as date of IMP dosing – date of last COVID-19 infection reported)
- Number of prior confirmed COVID-19 Infections
- Whether the previous COVID-19 infection led to hospitalization in the past 6 month or not

4.1.7 Medical History and Concomitant Disease

4.1.7.1 Definitions and Derivations

Clinically significant abnormal physical examination findings at screening will be recorded as medical history.

Medical history and relevant surgical history will be coded using the Medical Dictionary for Regulatory Activities (MedDRA) version 26.0 or later. The version used will be indicated in the data summaries and listings.

4.1.7.2 Presentation

Medical history and Concomitant disease will be grouped by MedDRA system organ class and preferred term and will be summarized in the Safety Analysis Set as number and percentage of participants in each treatment arm.

4.1.8 Prior and Concomitant Medications

4.1.8.1 Definitions and Derivations

Medications will be coded using World Health Organization Drug dictionary (WHO Drug) version Mar 2023 B3 or later. The version used will be indicated in the data summaries and listings.

Prior medications are any medications which stopped being taken prior to the study treatment.

Medication is considered concomitant if the start date is on or after the first IMP dosing date or if it started before the IMP dose and is ongoing after the IMP dose.

The algorithm for imputing missing or partial medication start and stop dates is provided in Appendix A.

4.1.8.2 Presentation

Prior and Concomitant therapy will be grouped by Anatomical Therapeutic Class (ATC) Level 2 and preferred drug name and will be summarized for all participants in the Safety Analysis Set as number of participants in each treatment arm and number of events.

4.1.9 Study Drug Compliance

4.1.9.1 Definitions and Derivations

There is only single study intervention administration in this study.

4.1.9.2 Presentation

Compliance will be reported in the disposition table as participants who were randomized but not dosed, and participants who received study intervention.

4.2 Endpoint Analyses

This section covers details related to the endpoint analyses such as primary, secondary, other endpoints including sensitivity and supportive analyses.

Statistical category	Endpoint	Population	Intercurrent event strategy	Population level summary (analysis)	Details in Section
Objective 1: To evaluate the safety of AZD3152 compared with Placebo					
Primary	Occurrence of AEs collected throughout the study	Safety analysis set	Treatment policy will be applied, i.e., all observed events collected will be included in the analysis.	The number and proportion of participants with AEs, SAEs, MAAEs, AESIs.	4.2.1
	Occurrence of SAEs, MAAEs, and AESIs collected throughout the study				
Objective 2: To compare the nAb responses to the SARS-CoV-2 emerging dominant variant(s) of concern circulating during the course of the study in serum following AZD3152 or Placebo administration					
Secondary	Titer for SARS-CoV-2 emerging dominant variant(s) nAbs	SARS-CoV-2 nAb analysis set	Participants who experience protocol deviation that can interfere with an antibody response or violate adherence to the assigned dose, become infected, receive COVID-19 treatment or vaccination that can alter nAb levels will have data collected after the intercurrent event set to missing for analysis of this endpoint (i.e., while-on-treatment strategy is applied).	Geometric mean titer (GMT) and geometric mean fold rise (GMFRs) (from baseline value through Day 181 after the single IM dose) of SARS-CoV-2 nAbs. Descriptive statistics for the log-transformed titer will include the number of participants, GMT and GMFR, corresponding gSD, 95% CI, minimum, and maximum and summarized by treatment arm.	4.2.2
Objective 3: To compare the incidence of symptomatic COVID-19 cases in participants receiving study intervention.					
Secondary	Incidence of a post-treatment symptomatic COVID-19 case (negative RT-PCR at baseline to	Full analysis set	Participants who become unblinded to treatment assignment and/or take other non-investigational product(s) for COVID-19	Incidence of a post-treatment symptomatic COVID-19 case.	4.2.3

Statistical category	Endpoint	Popu-lation	Intercurrent event strategy	Population level summary (analysis)	Details in Section
	positive RT-PCR or positive antigen test at any time up to 6 months AND symptoms specified in the modified WHO definition of symptomatic COVID-19).		prevention, in both cases prior to having met the criteria for the COVID-19 endpoint, will have data collected after the intercurrent event set to missing for analysis of this endpoint (i.e., while-on-treatment strategy is applied).		
Objective 4: CCI					
Exploratory	CCI				
Objective 5: CCI					
Exploratory	CCI				

AE = adverse event; AESI = adverse event of special interest; CI = confidence interval; GMFR = geometric mean fold rise; GMT = geometric mean titer; gSD = geometric standard deviation; IMP = investigational medicinal product; MAAE = medically attended adverse event; nAb = neutralizing antibody; RT-PCR = reverse transcription polymerase chain reaction; SAE = serious adverse event; SARS-CoV-2 = severe acute respiratory syndrome coronavirus 2; WHO = World Health Organization

4.2.1 Primary Endpoints

Primary endpoints are:

- Occurrence of AEs collected through the study
- Occurrence of SAEs, MAAEs, and AESIs collected throughout the study

4.2.1.1 Definition

For definition of AEs, SAEs, MAAEs, and AESIs see Section 8.3 of the CSP.

Adverse events will be collected from the time of study intervention administration through the last study visit.

MAAE, AESI will be recorded from the time of study intervention administration throughout the study, up to and including the last visit.

SAEs will be recorded from the time of signing of the ICF throughout the study, up to and including the last visit.

4.2.1.2 Derivations

AEs will be coded using the latest version of the MedDRA dictionary.

4.2.1.3 Primary Analysis of Primary Endpoint

Summaries of AEs, SAEs, MAAEs and AESIs per MedDRA System Organ Class (SOC) and Preferred Term (PT) will include the number and percentage of participants reporting at least one event and number of events.

Also all AEs will be presented in following tables:

- Overall summary of AEs
- AEs by SOC and PT
- AEs by SOC, PT, and maximum intensity
- Possibly related AEs by SOC and PT
- Immediate AEs after study intervention dose by SOC and PT
- COVID-19-related AEs by SOC and PT
- AESIs by category and PT
- Medically attended AEs by SOC and PT
- Serious AEs by SOC and PT
- Possibly related AESIs by category and PT
- Possibly related medically attended AEs by SOC and PT
- Possibly related serious AEs by SOC and PT

- Serious AESIs by category and PT
- Medically attended serious AEs by SOC and PT
- Possibly related serious AESIs by category and PT
- Possibly related medically attended serious AEs by SOC and PT
- AESIs – PT mapping (according to Appendix D)

The following listings will be presented:

- All AEs
- SAEs
- MAAEs
- AESIs
- AEs leading to death
- COVID-19 Initial Assessment AEs

4.2.2 Secondary Endpoint - SARS-CoV-2 Neutralizing Antibody Assessments

4.2.2.1 Definition

Serum samples to measure SARS-CoV-2 Neutralizing Antibody (nAb) levels will be collected according to planned visits. Authorized laboratory will measure nAbs to the SARS-CoV-2 emerging dominant variant(s) circulating during the course of the study.

The SARS-CoV-2 nAb responses include the nAb titer levels and fold rise of nAb titers collected over time. The fold rise will be calculated as the ratio of the post-dose titer and the baseline nAb titer levels.

This secondary endpoint will be analyzed in the SARS-CoV-2 neutralizing antibody analysis set.

4.2.2.2 Derivations

The geometric means will be calculated as the mean of the assay results after taking the logarithm transformation and then anti-logarithm transformation the mean to express results on the original scale. Two-sided 95% CIs will be obtained by taking log transforms of assay results, calculating the 95% CI with reference to Student's t-distribution, and then anti-logarithm transforming the confidence limits.

Geometric mean fold rises (GMFRs) will be reported and limited to participants with non-missing values at both time points.

Dealing with missing and undetectable results (<LLOQ and >ULOQ) described in Appendix C. Participants who experience an important protocol deviation that can interfere with an antibody response or violate adherence to the assigned dose, become infected, receive COVID-19 treatment or vaccination that can alter nAb levels will have data collected after the intercurrent event set to missing for analysis of this endpoint (i.e., while-on-treatment strategy is applied).

4.2.2.3 Analysis

GMT and GMFRs, corresponding gSD, 2-sided 95% CIs, minimum and maximum will be presented for each visit by treatment arm in tables separately each dominant variant of SARS-CoV-2. Also box and whiskers plots (separately for each dominant variant) will be presented in the following manner: dots show geometric means, lines within boxes are medians, box bounds are quartiles and whiskers are minimums and maximums.

Also all data will be presented in listings.

4.2.3 Secondary Endpoint - Symptomatic COVID-19 Case

4.2.3.1 Definition

Incidence of a post-treatment symptomatic COVID-19 case (negative RT-PCR at baseline to positive RT-PCR or positive antigen test at any time up to 6 months AND symptoms specified in the modified WHO definition of symptomatic COVID-19).

This secondary endpoint will be analyzed in the FAS.

4.2.3.2 Derivations

The following criteria adapted from the WHO COVID-19 case definition clinical criteria (WHO 2022) will be used to determine a symptomatic COVID-19 case:

- Any two of the following: fever (subjective definition to be used for fever), cough, positive COVID-19 test (rapid antigen test or RT-PCR)

OR

- Acute onset of ANY THREE OR MORE of the following signs or symptoms: fever (subjective definition to be used for fever), cough, general weakness/fatigue, headache, myalgia, sore throat, coryza, dyspnea, nausea/diarrhea/anorexia, conjunctivitis, positive COVID-19 test, symptom as judged by the Investigator to be related to COVID-19.

To properly link the onset of symptoms with the laboratory results, a window will be applied to the symptom onset date. For participants who meet the symptomatic criteria listed above, a positive of RT-PCR test or positive antigen test collected within 10 days of COVID-19 symptoms is required to consider the participant meeting the symptomatic COVID-19 case criteria.

Participants who become unblinded to treatment assignment and/or take other non-investigational product(s) for COVID-19 prevention, in both cases prior to having met the criteria for the COVID-19 endpoint, will have data collected after the intercurrent event set to missing for analysis of this endpoint (i.e., while-on-treatment strategy is applied).

4.2.3.3 Analysis

The following results will be presented with descriptive statistics by treatment arm:

- Participants who has symptomatic COVID-19
- Time to event of symptomatic COVID-19
- Participants with COVID-19 symptoms up to Visit 6 (Day 181)

Also all data will be presented in listings.

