If, following study intervention administration, a subject develops COVID-19, according to the Provisional recommendations on the methods for prevention, diagnosis and treatment of novel coronavirus infection (COVID-19), issued by the Ministry of Health of the Russian Federation, version 17 dated December 14, 2022 (Provisional recommendations 2022) (s)he must call “122” to be visited by a healthcare professional who, among other procedures, will perform a COVID-19 test. Once a visit by a healthcare professional has been requested, the subject must notify the study doctor of the date symptoms occurred and the date a healthcare professional visit has been requested, as soon as possible. Also, once a test result is available, the participant must report within 3 days the date of test and its result to the Investigator. If the test result is positive, the Investigator (or his/her delegate, according to the local regulations and institution guidelines) will make telephone calls **every three days** to collect safety data until the subject informs about his/her recovery.

Participants can receive SARS-CoV-2 vaccines after the Day 29 assessments.

Overall study design is described in [Figure 1](#).

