##### **9.4.2.2 Secondary Endpoint(s)**

###### **Secondary endpoint: Titer for SARS-CoV-2 emerging dominant variant(s) nAbs.**

Corresponding endpoints are GMTs and GMFTs for SARS-CoV-2 emerging dominant variant(s) nAbs.

Intercurrent events: Participants who experience a protocol deviation that can interfere with an antibody response or violate adherence to the assigned dose, become infected, receive COVID-19 treatment or vaccination that can alter nAb levels will have data collected after the intercurrent event set to missing for analysis of this endpoint (i.e., while-on-treatment strategy is applied).

SARS-CoV-2 neutralizing antibody analysis set will be used for the analysis of this endpoint.

Descriptive statistics for the log-transformed titer will include the number of participants, GMT and GMFR, corresponding gSD, 95% CI, minimum, and maximum and summarized by treatment arm, visit and optionally by virus variant.

The dominant SARS-CoV-2 variants circulating during the study will be identified by the time of analysis.

Summary measures for nAb responses against the emerging dominant variant circulating during the course of the study will be presented as GMT and GMFR at each scheduled visit involving collection of the relevant biosamples.

GMT and GMFT will be descriptively compared between treatment arms.

**Secondary endpoint: incidence of a post-treatment symptomatic COVID-19 case** (negative RT-PCR at baseline to positive RT-PCR or positive antigen test at any time up to 6 months AND symptoms specified in the modified WHO definition of symptomatic COVID-19).

Intercurrent events: Participants who become unblinded to treatment assignment and/or take other non-investigational product(s) for COVID-19 prevention, in both cases prior to having met the criteria for the COVID-19 endpoint, will have data collected after the intercurrent event set to missing for analysis of this endpoint (i.e., while-on-treatment strategy is applied).

The numbers and percentages of symptomatic COVID-19 cases up to 6 months will be presented. Treatment arms will be descriptively compared by corresponding variables.

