3.3.1 General Study Level Definitions

The study will consist of 2 periods: a screening period of up to 7 days (Day -7 through Day -1), and a treatment and follow-up period lasting 6 months after the administration of study intervention which consist of Visit 1 (Day 1), Visit 2 (Day 8), Visit 3 (Day 15), Visit 4 (Day 29), Visit 5 (Day 91) and Visit 6 (Day 181). Acceptable visit windows presented in Section 3.3.2. More detailed description of study visits and procedures presented in the Schedule of Activities (Table 1) of the CSP.

Categorical variables will be summarized using frequency, percentages (where the denominator for calculation is the underlying analysis set population, unless otherwise stated).

Continuous (quantitative) data will be presented as:

- Number of valid observations (n);
- Arithmetic Mean (M) or Geometrics Mean (gM) if appropriate;

- Standard deviation (SD) or Geometric standard deviation (gSD) if appropriate;
- 95% confidence interval (CI) if appropriate;
- Minimum value (Min.);
- Maximum value (Max.);
- Median (Me);

Data after log transformation will be rounded up to 3 decimals.

For continuous data, descriptive statistics will be rounded according to rules:

Mean, geometric mean, median and quartiles will be represented with an accuracy of 1 decimal place greater than the measured values. Standard deviation and geometric standard deviation will be represented with an accuracy of 2 decimal places greater. Minimum and maximum will have the accuracy of the measured values.

For categorical data, percentages will be rounded to 1 decimal place.

Data will be provided in data listings sorted by treatment arm and participant number. Tabular summaries will be presented by the actual treatment received for safety analysis and by the assigned for efficacy analysis.

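### SAP 4.2.3.3 summarises time to symptomatic COVID-19 with descriptive statistics and no censoring rule; read as written, the line covers cases only and says almost nothing about protection

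*SAP*

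**What the plan says.** SAP 4.2.3.3 opens with "The following results will be presented with descriptive statistics by treatment arm" and then lists three items: participants with symptomatic COVID-19, "Time to event of symptomatic COVID-19", and participants with COVID-19 symptoms up to Day 181. All data are also to be listed.

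The only general definition of descriptive statistics for a quantitative variable is in SAP 3.3.1. Under "Continuous (quantitative) data will be presented as" it lists the number of valid observations, mean, SD, 95% CI if appropriate, minimum, maximum and median.

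The summary measure for the efficacy objective is incidence. Protocol 9.4.2.2 says: "The numbers and percentages of symptomatic COVID-19 cases up to 6 months will be presented". SAP 3.3.4 adds: "All analyses will be performed in descriptive manner, no hypothesis testing will be performed".

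Follow-up for this endpoint can end early. Under SAP 4.2.3.2, participants who are unblinded or take another product for COVID-19 prevention before becoming a case "will have data collected after the intercurrent event set to missing for analysis of this endpoint". Protocol 4.1 states: "Participants can receive SARS-CoV-2 vaccines after the Day 29 assessments". Protocol 6.3.2 lets the code be broken for a participant who wishes to be considered for a vaccine. SAP 3.3.2 places Visit 6 anywhere from Day 167 to Day 195 for nAb samples.

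**The concern.** A participant who never develops COVID-19 has no event time. If the SAP 3.3.1 list is applied to this variable as it stands, n is the number of cases, and the mean and median describe day of onset among cases. The two arms are then compared on subsets selected by the outcome, and everyone who stayed free of disease drops out.

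Such a figure reflects when cases happen, not how many are prevented. A strongly protective product and an inert one give nearly the same value. If protection is strong early and weaker later, the surviving cases fall late and the figure looks like a benefit. The line would sit beside the case count under the efficacy objective, where readers will compare arms on it.

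**Working it through.** **The plan's own figures.** Neither document gives an expected value for this variable, so there is none to reproduce. The arm sizes do reproduce: 108 / 0.95 = 113.7, so 114, and the next multiple of 4 for 3:1 allocation is 116, that is 87 and 29 (Protocol 9.2 and the synopsis). They were set on adverse-event detection, not on COVID-19 cases.

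**Inputs.**
- n = 87 (AZD3152) and 29 (placebo).
- Follow-up T = 180 days (Day 1 to Day 181).
- Efficacy 83%, applied to the hazard. Protocol 2.3.2 gives this for the related product EVUSHELD, not for AZD3152. Protocol 2.2.2 gives 76.73% for the same product.
- Six-month placebo incidence F: not in the documents. Assumed, range 2% to 30%.
- Constant hazard, except in the waning example.

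**Formulas.** With L = −ln(1 − F):
- mean onset among cases = T × [1/L − (1 − F)/F];
- active arm: L1 = 0.17 × L and F1 = 1 − exp(−L1);
- restricted mean event-free time, all participants = T × F/L.

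**Example, F = 10%.**
- Placebo: L = 0.10536; mean = 180 × (9.4912 − 9.0000) = 88.4 days.
- AZD3152: L1 = 0.017911, F1 = 0.017752; mean = 180 × (55.8307 − 55.3322) = 89.7 days.

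**Range** (placebo vs AZD3152; differences taken before rounding):

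| Placebo incidence | Mean onset among cases, days | Difference, days | Cumulative incidence | Restricted mean event-free time, days |
|---|---|---|---|---|
| 2% | 89.7 vs 89.9 | 0.3 | 2% vs 0.3% | 178.2 vs 179.7 |
| 5% | 89.2 vs 89.9 | 0.6 | 5% vs 0.9% | 175.5 vs 179.2 |
| 10% | 88.4 vs 89.7 | 1.3 | 10% vs 1.8% | 170.8 vs 178.4 |
| 20% | 86.7 vs 89.4 | 2.8 | 20% vs 3.7% | 161.3 vs 176.6 |
| 30% | 84.7 vs 89.1 | 4.4 | 30% vs 5.9% | 151.4 vs 174.7 |

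With 76.73% efficacy the cases-only difference runs from 0.2 to 4.1 days. Cumulative incidence, which keeps everyone in the risk set, shows the effect plainly in each row.

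**Noise.** At 10% incidence and 83% efficacy:
- Expected cases are 29 × 0.10 = 2.9 on placebo and 87 × 0.01775 = 1.5 on AZD3152.
- The chance of no case, hence no statistic, is 0.90^29 = 5% and (1 − 0.01775)^87 = 21%. The chance of at most one case, hence no SD, is 20% and 54%.
- In 40,000 simulated trials, both arms had a case in 75%. Among those, the AZD3152 mean was earlier than placebo in 49%, and the 95% range of the difference was −103 to +107 days. With no efficacy at all, the AZD3152 mean was earlier in 50%.

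**Waning.** Keep placebo at 10% and split follow-up into two 90-day halves.
- Efficacy 90% then 50% puts about 0.10/(0.10 + 0.50) = 1/6 of cases in the first half. The mean is about 45 × 1/6 + 135 × 5/6 = 120 days (119.6 exactly).
- Efficacy 50% then 90% gives about 60 days (59.6 exactly).
- Cumulative incidence is the same in both: 1 − exp(−0.10536 × 0.30) = 3.1%. Placebo is at 88.4 days. Waning protection therefore reads as a delay of about 31 days (119.6 − 88.4), and the mirror image reads as harm.

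**The case against.** The SAP does not say that the summary is among cases. The term time to event usually implies censoring, Kaplan-Meier quantiles are themselves descriptive, and SAP 3.3.1 speaks of continuous data in general. That stands: a reader might infer that the SAP prescribes a cases-only comparison, but this is the natural reading rather than a stated rule. It does not make the line adequate. The SAP spells out its other derivations, such as GMTs and their intervals (4.2.2.2), follow-up duration (4.3.1.1) and time since last infection (4.1.6.1), and gives nothing here. It does not even say whether the event date is symptom onset or the positive test, which 4.2.3.2 allows to be up to 10 days apart. If non-cases were given their follow-up time instead, a mean would mix event and censoring times and would also be invalid.

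A reader might also infer that the efficacy assessment as a whole is unsound. The documents do not support that. The summary measure is incidence, case counts appear in the same list, nothing is tested, and the primary objective is safety.

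Kaplan-Meier is not free of difficulty. With about three cases or fewer per arm at 10% incidence, its estimates will be imprecise. Censoring at unblinding or at other COVID-19 prevention targets incidence as if those events had not occurred, whereas the documents name a while-on-treatment strategy. It also assumes that this censoring is independent of risk, which is open to doubt when participants may be unblinded because they want a vaccine. These points stand and must be stated with the method. A labelled description of onset days among cases is also legitimate.

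**Conclusion.** The point holds for a supportive descriptive line. On the readable text the variable has no time origin, event date, censoring rule or estimator. The stated statistics, applied literally, give a comparison between cases that barely responds to protection: 0.3 to 4.4 days for an 83% hazard reduction. The figure follows the timing of protection rather than its amount.

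The size rests on an assumed placebo incidence of 2% to 30%, a constant hazard and efficacy borrowed from the related product. The conclusion is the same across that range. The incidence numbers and percentages, the safety objective and the sample size are unaffected. Redacted exploratory text in SAP 4.2.4 could not be judged. The change is worth making, but no main result depends on it.

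**What to change.** In SAP 4.2.3.3:
- Define time from dosing to a stated event date, either symptom onset or first positive test.
- Show Kaplan-Meier cumulative incidence by arm with numbers at risk and confidence intervals at Days 29, 91 and 181. Censor at the earliest of intercurrent event, last contact and Day 181.
- State that this assumes censoring at unblinding or other COVID-19 prevention is independent, say how it relates to the while-on-treatment strategy, and note that few cases will make the estimates imprecise.
- Keep individual onset days in the listing. If an onset-day summary is kept, label it as among cases only and not a measure of efficacy.

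The cost is a few sentences of SAP text and one standard table or figure. It needs no additional data collection beyond dates of dosing, symptoms, tests, intercurrent events and last contact.
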